11.3.2. Age

Age: age at the reference activity is computed as the number of units between the date of birth and the reference activity, expressed in months/years.

When age at reference activity is to be displayed in months/years, it will be calculated as the number of complete calendar months/years between the date of birth and the date of reference activity. For example:

- DOB = 10JUN2017, Date of vaccination = 09JUL2018 -> Age = 12 months
- DOB = 10JUN2017, Date of vaccination = 10JUL2018 -> Age = 13 months
- DOB = 10SEP1983, Date of reference = 09SEP2018 -> Age = 34 years
- DOB = 10SEP1983, Date of reference = 10SEP2018 -> Age = 35 years

11.3.3. Follow-up/duration

Follow-up time in a month will be computed as the total number of follow-up days in the month. For instance, a subject with follow-up start on 30 September (last day of the month) will contribute by 1 day. The follow-up will be converted in month by dividing by 12 or will be converted in year by dividing by 365.25.

Duration of an event is expressed in days. It is the number of days between the start and the stop dates + 1. Therefore, duration is 1 day for an event starting and ending on the same day.

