7.2.2. Additional considerations

7.2.2.1. Incidence rate

In light of the low number of dengue episodes, the large number of positive anti-dengue IgG at visit 1 and the number of dengue cases reported outside the season,

1. The analyses of PCR confirmed cases (only 10 cases) and the analyses of secondary dengue infections were removed.
2. The analyses by seroprevalence at each visit were removed,
3. The analyses by season were removed. Only the analyses by calendar year are to be conducted

- 4. Subjects without seroprevalence status at visit 1 were removed from the ATP cohort because serological status of symptomatic/inapparent dengue infections cannot be assessed properly for such subjects
- 5. Planned analyses of medical and vaccination history were removed.
- 6. The statistical method was updated to ignore the household cluster effect and to provide incidence rate with confidence interval in absence of dengue episodes in a calendar year for a study site .

Regarding the last point, the expected annual incidence rate for a cohort of subjects followed over a full calendar will be computed using a log-linear model with the number of dengue events (all cases) as depend variable and the total number of subject-month as offset. The model will include the study site, year and month as independent categorical fixed effects (see below).

The expected annual incidence rate in a study site for each year will be estimated as the average of incidence rate over months

```

proc genmod ;
  class center month year;
  model evt= center year month /
    dist=poisson link=log offset=ln TYPE3;

  ods output Estimates=estimc;
  estimate 'center PPD 2014' intercept 12 center 12 0 0 0 0
    year 12 0 0 0 0
    Month 1 1 1 1 1 1 1 1 1 1 1;
  estimate 'center PPD 2014' intercept 12 center 0 12 0 0 0
    year 12 0 0 0 0
    Month 1 1 1 1 1 1 1 1 1 1 1;
  estimate 'center PPD 2014' intercept 12 center 0 0 12 0 0
    year 12 0 0 0 0
    Month 1 1 1 1 1 1 1 1 1 1 1;
  estimate 'center PPD 2014' intercept 12 center 0 0 0 12 0
    year 12 0 0 0 0
    Month 1 1 1 1 1 1 1 1 1 1 1;
  estimate 'center PPD 2014' intercept 12 center 0 0 0 0 12
    year 12 0 0 0 0
    Month 1 1 1 1 1 1 1 1 1 1 1;
  estimate 'overall 2014' intercept 12 center 2.4 2.4 2.4 2.4 2.4
    y 12 0 0 0 0
    Month 1 1 1 1 1 1 1 1 1 1 1;
  estimate 'center PPD 2015' intercept 12 center 12 0 0 0 0
    year 0 12 0 0 0
    Month 1 1 1 1 1 1 1 1 1 1 1;
  estimate 'center PPD 2015' intercept 12 center 0 12 0 0 0

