```

```

estimate 'overall' intercept 60 center 12 12 12 12 12
                        year 12 12 12 12 12
                        Month 5 5 5 5 5 5 5 5 5 5 5 5;
estimate 'overall center PPD' ' intercept 60 center 60 0 0 0 0
                        year 12 12 12 12 12
                        Month 5 5 5 5 5 5 5 5 5 5 5 5;
estimate 'overall center PPD' ' intercept 60 center 0 60 0 0 0
                        year 12 12 12 12 12
                        Month 5 5 5 5 5 5 5 5 5 5 5 5;
estimate 'overall center PPD' ' intercept 60 center 0 0 60 0 0
                        year 12 12 12 12 12
                        Month 5 5 5 5 5 5 5 5 5 5 5 5;
estimate 'overall center PPD' ' intercept 60 center 0 0 0 60 0
                        year 12 12 12 12 12
                        Month 5 5 5 5 5 5 5 5 5 5 5 5;
estimate 'overall center PPD' ' intercept 60 center 0 0 0 0 60
                        year 12 12 12 12 12
                        Month 5 5 5 5 5 5 5 5 5 5 5 5;

run;
    
```

```

data estimc; set estimc;
    if label='overall' or index(label,'overall center') then do;
        estimate=exp(lbetaestimate/60);
        lower=exp(lbetalowercl/60);
        upper=exp(lbetauppercl/60);
        end;
    else do;
        estimate=exp(lbetaestimate/12);
        lower=exp(lbetalowercl/12);
        upper=exp(lbetauppercl/12);
        end;
run;
    
```

In case of subgroup analysis by gender or by age at visit 1 (<=17years, 18-49 years and >= 50years) or in case the model does not allow estimating confidence interval (eg problem of convergence or situation where there is no event in a site, in a calendar year or in a month) CI will be computed using exact CI based on a Poisson Distribution.

The following case provides the SAS code for the exact CI for incidence rate per subject-year when there are 14 events and 400 subject-years:

```

data check;
    fu=400;
    n=14;
    Rate=n/fu;
    LL_rate= GAMINV(0.025, n)/fu;
    UL_rate= GAMINV(0.975, (n+1))/fu;
    LL_rate_=cINV(0.025, 2*n)/(2*fu);
    UL_rate_=cINV(0.975, 2*n+2)/(2*fu);
    
```

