11. DATA DERIVATION RULES AND STATISTICAL METHODS

11.1. Data presentation

The following decimal description will be used for the analyses:

Display Table	Parameters	Number of decimal digits
Dengue cases	Incidence rate (in 1000 person-years) with LL & UL, person-years	1
Dengue cases	% of count, including LL & UL of CI	1
Dengue cases	Minimum, maximum, range	Number of decimals in the raw data
Dengue cases	Mean, median	Number of decimals in the raw data +1
Dengue cases	SD	Number of decimals in the raw data +2
Hematology/biochemistry	%	1
Demographic/baseline characteristics and changes between scheduled visits	Percentage, mean, median, standard deviation, minimum, maximum, Q1, Q3	1

CI = confidence interval

LL = lower limit of the confidence interval

SD = standard deviation

UL = upper limit of the confidence interval

Q1/Q3 = 25th and 75th percentiles

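### SAP 11.3.3 converts follow-up days to months by dividing by 12; programmed as written, subject-months are 2.54 times too large and model-based rates 60.6% too low

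*SAP*

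**What the plan says.** All references are to SAP Amendment 1 unless another document is named.

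- **Unit of follow-up (11.3.3).** "Follow-up time in a month will be computed as the total number of follow-up days in the month". The section's own example, a subject who starts on 30 September and contributes one day, confirms that the count is in days.
- **Conversion (11.3.3).** "The follow-up will be converted in month by dividing by 12 or will be converted in year by dividing by 365.25".
- **Use of the month unit (7.2.2.1).** The log-linear Poisson model has "the total number of subject-month as offset", with site, year and month as fixed effects.
- **What the model is said to give (7.2.2.1).** "The expected annual incidence rate in a study site for each year will be estimated as the average of incidence rate over months". The back-transformation line begins "estimate=exp(lbetaestimate/12" (60 replaces 12 for the all-years contrasts).
- **Alternative method (7.2.2.1).** Exact Poisson limits are used for gender and age subgroups, and when the model cannot give an interval, for example on non-convergence or in a "situation where there is no event in a site, in a calendar year or in a month". The code supplied is for an "exact CI for incidence rate per subject-year when there are 14 events and 400 subject-years".
- **Reporting unit (11.1).** "Incidence rate (in 1000 person-years) with LL & UL, person-years".

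**The concern.** One sentence applies two divisors to the same day count, and they cannot both be right. A subject followed for 365.25 days would have one year of follow-up but 30.4 months, and a 30-day month would count as 2.5 months. Dividing by 12 turns months into years; it does not turn days into months.

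The rule is not incidental. Subject-months are the exposure in the model that produces the site, year and overall rates. The primary objective is to estimate incidence, and section 8 says that all analyses are descriptive, so the absolute rate is itself the result. Protocol section 1.2 says the study is meant to validate attack-rate assumptions for later efficacy trials, where the absolute level is what counts.

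A gap beside the rule makes the slip harder to notice. The back-transformation only undoes the 12-fold (or 60-fold) contrast weights. It gives a rate per unit of the offset, that is, per subject-month. The SAP calls this annual and reports per 1000 person-years, but shows no step from one to the other.

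**Working it through.** **1. The divisor.** From 11.3.3, one year is 365.25 days. One month is therefore 365.25/12 = 30.4375 days. No calendar month length gives 12. The 14 June 2019 SAP (12.4.3) divides days by 30.4375 for intervals between visits. That is a different rule, so it supports the corrected number but does not prove what was intended here.

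**2. Size of the error.**
- Inflation of subject-months: 30.4375/12 = 2.536.
- Effect on the rate per subject-month: 12/30.4375 = 0.394, a fall of 60.6%.
- Effect on the log scale: the offset rises by ln(2.536) = 0.931 in every cell and the intercept falls by the same amount.
- Sensitivity to month length: with 28 to 31 days per month the inflation is 2.33 to 2.58 and the fall is 57.1% to 61.3%.

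**3. The SAP's own example (7.2.2.1): 14 events in 400 subject-years.** The exact method gives 14/400 = 0.0350, with limits GAMINV(0.025, 14)/400 = 0.0191 and GAMINV(0.975, 15)/400 = 0.0587. That is 35.0 per 1000 person-years (95% CI 19.1 to 58.7). The same follow-up is 400 × 365.25 = 146,100 days:

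| | Divisor 30.4375 | Divisor 12 |
|---|---|---|
| Subject-months | 4,800 | 12,175 |
| Events per 1000 subject-months | 2.92 | 1.15 |
| Multiplied by 12: per 1000 person-years | 35.0 | 13.8 |

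The last row assumes a multiplication by 12 that the SAP does not show. With it, the corrected divisor agrees with the exact method and the written one does not.

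**4. At the planned incidence level.** Protocol 8.2.1 expects about 10 per 1000 person-years. That is 10/12 = 0.833 per 1000 true subject-months, but 10 × 12/365.25 = 0.329 with the written divisor. If then multiplied by 12, it would print as 3.9 per 1000 person-years. Likewise 9 per 1000 would print as 9 × 0.394 = 3.5, outside the interval of 6.3 to 11.7 that protocol 8.2.3 gives for 9 per 1000 with four years of follow-up.

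**5. Check through the model.** The SAP's model was fitted to simulated counts (5 sites, 5 years, 12 months) with each divisor, using a 12-month contrast and the SAP's back-transformation. The estimate and limits were 0.00456 (0.00361 to 0.00575) with 30.4375 and 0.00180 (0.00142 to 0.00227) with 12. All three were multiplied by 0.394. The intercept moved by 0.931; the other coefficients and all standard errors did not change.

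**The case against.** The strongest objection is that this may be a drafting slip that never reached a result.

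- **The program is not shown.** The model code takes a pre-computed log offset. The programmer may have used 30.4375, and the year conversion beside it is correct. This stands: the documents show a wrong rule, not a wrong result. Person-years displayed in the same table might also expose a scale error, but only to a reader who recomputes the rates.
- **The model may be little used.** The SAP stresses the low number of dengue episodes, and one site, year or month without an event is enough to move to the exact method. This stands too. The event distribution is not given, so the affected output could be everything outside the subgroup tables or nothing.
- **The dependent variable is all cases, while the primary objective concerns laboratory-confirmed cases.** The SAP does not say what all cases covers, so the link to the primary endpoint is not fully spelled out. Even so, 7.2.2.1 gives no other method for the overall, site and year incidence rates.
- **The worked figures are crude rates.** The model averages log rates over months, which gives a geometric mean, so its absolute output equals the crude rate only if the monthly rates are equal. This is correct, but the factor 0.394 applies either way.
- **The 2.54-fold gap to the exact rates needs a conversion to person-years.** It does. With no such step the gap in the example of 10 per 1000 person-years would be 10/0.329 = 30.4-fold. The 2.54-fold gap is the one left once both are put in the reporting unit of 11.1.

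**Conclusion.** The rule in 11.3.3 is wrong as written and should be corrected before the results are relied on. If it was programmed literally, the model-based rates and both confidence limits are 60.6% too low (factor 0.394), and subject-months are 2.54 times too large. Overall and site rates from the model could then differ 2.54-fold, through units alone, from exact subgroup rates in the same report. Relative comparisons among sites, years and months are unaffected, which is why model diagnostics would not show the problem.

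The size rests on the SAP's own year of 365.25 days. The effect on reported results rests on two things the documents do not settle: that the offset was derived by the written rule, and that the model rather than the exact method was used.

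**What to change.** 1. In 11.3.3, divide days by 30.4375 for months and by 365.25 for years. Alternatively, use subject-years as the offset throughout, so that the model and the exact method share one unit.
2. In 7.2.2.1, state the unit of the offset variable and the step from the back-transformed estimate to a rate per 1000 person-years. Correcting the divisor alone does not close this gap.
3. Check the program that derives the offset against the corrected rule, and rerun the model-based rates if it divided by 12.

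The cost is one number, one sentence and a program check. No new data are needed.

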11.3.4. Moderate to severe dengue cases

A moderate to severe case of dengue is defined as follows (in accordance to the “dengue with warning signs” and “severe dengue” definitions in the 2009 WHO guidelines for dengue):

One or more of the WHO 2009 warning signs or one or more of the WHO 2009 criteria for severe dengue are met (i.e. criteria box ticked in the eCRF):

Warning signs:

- Abdominal pain or tenderness
- Persistent vomiting
- Clinical fluid accumulation
- Mucosal bleed
- Lethargy, restlessness
- Liver enlargement >2 cm
- Laboratory: increase in hematocrit (HCT) concurrent with rapid decrease in platelet count

Criteria for severe dengue:

- Severe plasma leakage leading to:
 - Shock (Dengue Shock Syndrome)
 - Fluid accumulation with respiratory distress
- Severe bleeding as evaluated by clinician
- Severe organ involvement
 - Liver: Alanine aminotransferase (ALT) or Aspartate aminotransferase (AST) ≥ 1000
 - Central Nervous System (CNS): Impaired consciousness
 - Heart and other organs

1. DOCUMENT HISTORY

[figure not shown]
Date	Description	Protocol Version
14 JUN 2019	Final version	Amendment 3: 09 JAN 2015

2. STUDY DESIGN

2.1. Study design overview

- **Type of design:** Prospective, multicenter, community-based, household-sampling, cohort study in Brazil.
- **Duration of the study:** The study period per initial site, initially planned to be one year, was planned to be extended by additional three years (overall four years) to cover three additional dengue seasons. The study period for any new site was planned to be 3 years.
- **Enrolment wave:** There were 2 waves of enrolment for recruiting the planned 3600 subjects:
 - Initial Cohort = about 1800 subjects planned – four years follow-up planned – INITIAL sites: Rio (PPD), Manaus (PPD) and Salvador (PPD).
 - Expansion Cohort = about 1800 subjects planned – three years follow-up planned – planned NEW sites: Natal (PPD), Campo Grande (PPD), and Campinas (PPD).
- **Replacement:** replacement subjects were enrolled in order to compensate for subjects who did not wish to extend their participation for three additional years (for subjects from the initial cohorts), subjects who prematurely terminated participation or subjects who were lost to follow-up (for subjects from the initial and expansion cohorts).
- This was done to maintain a cohort size of at least 500 subjects per site, in the initial and expansion cohorts, at the beginning of each additional study year/season.

• **Schematic representation of the scheduled visits:**

V=Visit

The scheduled visits for initial cohort subjects are shown in black

New enrolments were to be done yearly (as needed) till the end of study Year 3 of each study site

Enrollment of expansion cohort subjects started preferably during study Year 2

For replacement subjects, the number of visits depended on the year enrolled

- **Type of study:** self-contained.
- **Data collection:** Electronic Case Report Form (eCRF).
- **Study termination:** in December 2017, GSK decided to deprioritise the development of the dengue purified inactivated vaccine (DPIV) candidate and to terminate the study EPI-DENGUE-006 at the study visit planned after the 2018 dengue season. This decision was made due to the scientific challenges and development risks associated with the candidate vaccine. The planned study site in Campo Grande was not initiated before the decision of study termination was taken, so no subjects were enrolled in that site.

2.2. Study population

This study planned to enrol subjects (six months of age and older at the time of enrolment) from randomly selected households from different communities within the selected sites.

2.2.1. Selection of study sites

Five sites covering different regions of the country were selected for this study. Selection criteria of the sites include support from the Family Health Physician Program (FHP), the Larval Index Rapid Assay (LIRA) or with field research experience in the community. Other selection criteria of the sites include an extensive feasibility assessment that includes aspects related to the site structure including laboratory and local facilities, availability of the principal investigator and previous experience on Dengue.

The FHP is a Brazilian government public health strategy that consists of multidisciplinary teams of health care workers that cover geographically defined areas to provide basic/preventive care to community members. The teams include a doctor, a nurse, a nurse auxiliary, and community health care workers who pay regular visits to the

household under its responsibility to deliver health promotion activities and facilitate triage and referral into the health unit, among other activities. Community health care workers are local residents who are trained for basic tasks.

LIRA is an alternative vector surveillance strategy that consists of random sampling of a number of dwellings in which surveillance of *Aedes*-positive breeding places is carried out to identify where there is a risk of mosquito reproduction, and has been widely implemented in Brazil [[Pontes, 2000](#)].

The study sites in Rio, Salvador, Natal and Campinas were selected mainly considering their experience in previous Dengue field research. Manaus was selected mainly for the experience of its principal investigator in dengue studies and the previous experience of the site in clinical trials with GSK.

At least one community of households within each site was selected.

2.2.2. Selection of communities

Community selection was based on the following characteristics: 1) preferably areas where the Brazilian FHP or LIRA has been fully implemented or where access to the community is already established by a government program, e.g., registry of families by Secretary of Health, or other institutional program, such as university, in order to allow for random sampling of households; 2) safe access by study personnel; 3) high population density; and 4) low migration rate.

2.2.3. Selection of households

Households were to be randomly selected through LIRA strategy or from a list provided by the FHP or equivalent.

The FHP or LIRA provided an exhaustive list of households to the study sites and served as the liaison between the study personnel and the household, and had not any other role in this study.

Sites with access to LIRA (i.e. Manaus, Natal and Campinas) use LIRA's specific sampling strategy. LIRA's sampling strategy (preferred strategy) consists of dividing the administrative neighbourhoods of the city into blocks in which each building is enumerated by a unique code number. Within each block a corner is chosen and moving leftward, one in every four houses is systematically selected for vector inspection.

Where LIRA was not implemented but has FHP coverage, a random sample of households was to be selected from the FHP database. Note that none of the five study sites part of the final analysis had FHP coverage.

Where another type of household registry offers the only access to the community (i.e. Rio and Salvador), a random sample was to be drawn from the registry database.

Actually, for Rio, Salvador, Natal and Campinas, contact in the communities was performed to identify potential subjects who were interested to be enrolled. In addition, households were selected based on their location (in more safety areas and near to the Unit of Health Care).

2.2.4. Selection of subjects

At least 3600 subjects were planned to be recruited in the study in 2 waves of enrolment. Each wave, initial and expansion cohorts, enrolled about 600 subjects per site in order to maintain at least 500 subjects per site at the beginning of each dengue season.

Preferably the recruitment period was planned to occur outside of the peak dengue transmission season, and continued until each site has reached its foreseen target. Recruitment of replacement subjects were done during the low dengue transmission.

If the target household was found empty or all members refused to participate, the first household to the left was approached. Those households refusing to participate were recorded as such. A household refusal was characterized when all individuals in the household refused to participate in the study. Individual refusals in a given household were not preclude inclusion of other individuals living in the households, and were recorded as such. Information on refusal was kept at the study site and was not recorded in the screening/enrolment log.

In the subsequent study years/seasons, the cohort size was maintained at a minimum of 500 subjects per site. Since subjects who prematurely terminate participation and/or lost to follow-up were replaced, the final number of participants across the four planned study years may exceed 3600 subjects. Yearly, there was an evaluation of active subjects. If the number of active subjects/site became < 500 , there were enrolment of replacement subjects to maintain a cohort size of at least 500 subjects per site. Recruitment of replacement subjects could have occurred at the end of the planned study year 1, 2 or 3. The recruitment approach was the same as for the initial enrolment. Replacement subjects were enrolled from households located in the same communities as the withdrawn subjects.

In order to better represent the Brazilian population distribution, subjects enrolled in the expansion cohorts should be composed of at least 30% of subjects younger than 18 years old and should not exceed 20 % of adults 50 years or older. Subjects enrolled as replacement subjects for the initial and expansion cohorts were recruited to approach as much as possible a minimal representation of 30% of subjects younger than 18 years old and a maximal representation of 20% for adults 50 years or older. This strategy was implemented at enrolment in Salvador, Natal and Campinas and for replacement subject in Rio.

